## 1.0 Study Summary

Study Title	Pilot Trial of a Motivational Interviewing and Cognitive Behavioral Therapy (MI-CBT) Ketogenic Nutrition Adherence Program for Older Adults
Study Design	Block Randomized Pilot Pragmatic Clinical trial completed virtually through HIPAA Compliant Zoom
Primary Objective	Assess feasibility and acceptability of all protocol components of a pilot pseudo-pragmatic trial testing a 6-week telehealth KNA program compared to a KN information only group for older adults with MCI in the FSU SeniorHealth clinic to prepare for a full-scale trial.
Secondary Objective(s)	Assess signal of initial effect of the KNA program on important clinical outcomes and adherence relative to a KN information-only condition.
Research Intervention(s)/Investigational Agent(s)	Using a centralized telehealth approach, the KNA program will consist of 6 weekly group meetings, which will take place via HIPAA-compliant Zoom. The group will be co-led by a clinical psychologist and a nurse practitioner with expertise in nutrition. Approximately half of each session will be devoted to providing nutrition information and half devoted to psychoeducation, MI activities, and CBT skills. Participants assigned to the KN-only group will also attend weekly group meetings with information about how to adhere to KN and how to track macronutrients, food intake, and ketone levels. Participants will be provided with the same participant binder as the KNA group with informational handouts and KN recipes, but without the MI-CBT handouts. Participants will be asked to track their food intake and daily ketone levels, and will be provided with the option of attending a weekly Zoom meeting where they may ask questions about KN and receive additional nutrition information as needed. These optional meetings will be offered for 6 weeks.
IND/IDE #	
Study Population	Older adults 60+
Sample Size	N = 60
Study Duration for individual participants	1 year, including pre/post assessments; intervention is 6 weeks.
Study Specific Abbreviations/Definitions	KN = ketogenic nutrition; KNA = ketogenic nutrition adherence; MCI = Mild Cognitive Impairment; PCT = Pragmatic clinical trial

## 2.0 Objectives\*

- **Objective 1:**

Assess feasibility and acceptability of all protocol components of a pilot pragmatic trial testing a 6-week telehealth KNA program compared to a KN information only group for older adults with possible or pre-MCI in the community and at a senior health clinic to prepare for a full-scale trial.

Specifically, we will examine the feasibility of the recruitment, retention, assessment, electronic health record (EHR) downloads, and intervention delivery methods through the FSU SeniorHealth™ clinic. If we determine it is not feasible to recruit the full sample through this clinic, we will expand recruitment to the community.

We hypothesize that

- *The study protocol (MI-CBT KNA program) will result in high patient retention (90%) and patient attendance of intervention sessions (80%), and*
- *A centralized MI-CBT telehealth delivery approach will be associated with high intervention acceptability ratings from patients and key stakeholders.*
- *MI-CBT KNA program will result in higher adherence to KN compared to the KN information-only group as evidenced by higher levels of ketones at week 6 of the intervention using at-home ketone urinalysis test strips.*

To test these hypotheses, we will use a mixed methods approach using qualitative interviews, quantitative measures of patient satisfaction with the intervention (using the Client Satisfaction Questionnaire) and provider perception of the overall fit of the intervention in the clinic, and of patient intervention attendance and study attrition. Qualitative data from providers and patients will be thematically coded to further examine acceptability and barriers to implementation.

- **Objective 2:**

Assess signal of initial effect of the KNA program on important clinical outcomes and adherence relative to a KN information-only condition.

We hypothesize that *patients in the KNA condition, relative to the KN-only condition, will show 1) higher rates of clinically significant improvements on the RBANS total scale scores, improvements in daily functioning (FSQ), decreases in patient CAIDE risk score, improvements in HbA1C levels and comprehensive metabolic panels, and improvements in self-reported pain using the Rolland-Morris Pain scale, and 2) improved adherence to KN, as evidenced by higher levels of measurable urine ketones in the KNA condition compared to the KN-only condition.*

*We will also examine the feasibility of using electronic health record (EHR) data as an additional measure of health, pain, and cognitive outcomes.*

To visually examine these hypotheses (as significance testing is not appropriate for a pilot study), we will extract data on clinical outcomes from the EHR to examine patient outcomes before and after engaging in the intervention and to compare group differences.

We expect that patients in the KNA condition will have higher rates of transferring to MCI or normal range on the RBANS and improvements in functional status on the FSQ. Participants in the KNA condition will have reductions in self-reported pain and greater improvements on other health indices. Additionally, we expect higher rates of measurable ketones (trace or higher) in the KNA program compared to KN-only based on daily, at-home urinalysis test strips. Combined, these data will provide important information about the clinical effects of the programs and feasibility of the proposed study components for a larger ePCT.

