#### **4.0 Study Endpoints\***

This study will focus on assessing the feasibility and acceptability of all protocol components of a pilot pragmatic trial, testing a 6-week telehealth KNA program compared to a KN information only group for older adults with possible MCI in the community and at a senior health clinic to prepare for a full-scale trial. We will use a mixed methods approach using qualitative interviews, quantitative measures of provider's perception of the overall fit of the intervention in the clinic, and of patient intervention attendance and study attrition. Qualitative data from providers and patients will be thematically coded to further examine acceptability and barriers to implementation.

We will also focus on assessing signal of initial effect of the KNA program on important clinical outcomes and adherence relative to a KN information-only condition. Data on clinical outcomes will be extracted or requested from patient health records before and after engaging in the intervention and to compare group differences. Patient participants will also complete assessments in-person, following appropriate COVID-19 precautions, pre- and post-intervention.

We expect that patients in the KNA condition will have higher rates of transferring to the normal range on the RBANS, greater improvements in functional status on the FSQ, and greater improvements in self-reported pain and other health indices. Additionally, we expect higher rates of measurable ketones (trace or higher) in the KNA program compared to KN-only based on daily, at-home urinalysis test strips. Combined, these data will provide important information about the clinical effects of the programs and feasibility of the proposed study components for a larger PCT.

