Baseline Assessment (Time 1). In addition to embedded EHR and other health record data, we are collecting additional data to evaluate the personal impacts of the intervention. This in-person assessment will include: the Repeatable Battery of Neuropsychological Status (RBANS update – form A), GAS, PHQ-9, FSQ, ISEL, MSQ, CAIDE risk score, OPQOL, GSE, PSQI, SCOFF, social support, self-efficacy, a verbal pain descriptor scale, the Brief Pain Inventory, The WOMAC-Pain scale, the PANAS, PSS, the WHY-MPI, and the Roland-Morris Pain and Pain-related Disability scale, a fasting blood draw for a comprehensive metabolic panel and HbA1C (completed by a certified medical assistant), a weight and body composition assessment, and basic vitals (blood pressure and heart rate). Participants will be scheduled in the morning for these assessments in order to allow approximately 10-hour fasting for the blood draw. This assessment will be completed in-person following COVID-19 precautions (described in section 14), and patient participants will be compensated \$30 for their time.

Post-intervention Assessment (Time 2). Participants will complete this assessment in the final weeks of the program, in order to assess participants when they are in ketosis. Participants will be asked to return their ketone logs either electronically, reported over the phone, or via mail to the study PI. The research team will complete qualitative interviews with participants to collect information about barriers and facilitators to completing the program and adhering to KN. Participants will complete the RBANS update – Form B, the PHQ-9, FSQ, MSQ, GAS, CAIDE risk score, OPQOL, PSS, PSQI, social support (ISEL), self-efficacy (GSE), group cohesion, a verbal pain descriptor scale, the Brief Pain Inventory, The WOMAC-Pain scale, the PANAS, the Roland-Morris Pain and Pain-related Disability scale, the WHY-MPI, and participants' global impression of change, a second fasting blood draw for comprehensive panels (completed by a certified medical assistant), a weight and body composition assessment, and basic vitals (blood pressure and heart rate). Participants will be scheduled in the morning for these assessments in order to allow approximately 10-hour fasting for the blood draw. This assessment will be completed in-person following COVID-19 precautions, and patient participants will be compensated \$30 for their time.

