Post-intervention Assessment (Time 3). Patient participants will complete this assessment approximately 3 months after completing the intervention program, in order to assess long-term maintenance. The research team will complete qualitative interviews with participants to collect information about barriers and facilitators to adhering to KN long-term. Participants will complete the RBANS Update – form C, the PHQ-9, FSQ, MSQ, GAS, CAIDE Risk score, OPQOL, PSQI, social support (ISEL), self-efficacy (GSE), a verbal pain descriptor scale, the Brief Pain Inventory, The WOMAC-Pain scale, the PANAS, PSS, the WHY-MPI, the Roland-Morris Pain and Pain-related Disability scale, the Client Satisfaction Questionnaire (8-item), and participants' global impression of change in pain. This assessment will be completed in-person following COVID-19 precautions and patient participants will be compensated \$30 for their time.

Participants who express barriers to completing the 3-month post-intervention assessment in person will have the option to complete this assessment remotely if they

choose to. In the even that a participant chooses to complete the Time 3 assessment remotely, the following procedures will be conducted: a research assistant will schedule a phone call with the participant at a time that is convenient to them to complete the qualitative interviews with participants and collect self-reported height, weight, and ketone test (if available); participants will be asked to complete questionnaires via REDCap by following a link to the survey that will be emailed to them by a team member; lastly, due to the nature of the RBANS, participants who choose to complete the Time 3 assessment remotely will not be asked to complete the RBANS Update – form C. Participants will receive the same amount of compensation, \$30, for their time upon completing the assessment procedures.

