## **11.0 Local Number of Subjects**

We are seeking to enroll a maximum of 60 participants and a minimum of 40 participants.

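### The expected RBANS effect is stated only as a responder or category-transfer rate, which makes the secondary cognitive signal from 40-60 people less precise than the collected total score allows

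*Protocol*

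**What the plan says.** The Protocol states the expected RBANS effect in three places.

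- Section 2.0 Objectives, Objective 2 hypothesis: "higher rates of clinically significant improvements on the RBANS total scale scores".
- Section 2.0 Objectives, expectations paragraph after Objective 2: "higher rates of transferring to MCI or normal range on the RBANS".
- Section 4.0 Study Endpoints: "higher rates of transferring to the normal range on the RBANS".

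Each is a proportion. None comes with a cut-off for clinically significant improvement or a boundary for the ranges, and none names a difference in score as the comparison.

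The score itself is available. Section 6.0 (Design Overview) lists RBANS form A at Time 1; at Time 2, "Participants will complete the RBANS update – Form B"; and form C at Time 3. The exception at Time 3 is that "participants who choose to complete the Time 3 assessment remotely will not be asked to complete the RBANS Update – form C".

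On size, section 11.0 says "We are seeking to enroll a maximum of 60 participants and a minimum of 40 participants". Section 12.0 assigns 30 to each condition at the maximum. Section 2.0 says the Objective 2 hypotheses will be examined visually and that significance testing does not suit a pilot.

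**The concern.** Objective 2 looks for a first signal of effect, and the pilot as a whole prepares for a full-scale trial. A yes/no version of a continuous score treats two people just either side of the cut as opposite results, and counts a large gain the same as a marginal one. With at most 30 per arm, a difference in rates is noisier than a difference in scores, so a real cognitive benefit is more likely to look absent, reversed or wrongly sized.

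The protocol gives no clinical or regulatory reason for using a rate here. Agreeing a single cut would not remove the loss, so this is separate from the fact that the three statements define the rate differently.

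**Working it through.** **Nothing to reproduce.** The protocol gives no effect size, SD, responder rate, cut-off or power for the RBANS, and no derivation of the sample size.

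**Inputs from the protocol.** N = 40 to 60, equal allocation, hence 20 to 30 per arm.

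**Assumptions.** Roughly normal scores with equal SD in both arms, and a responder share p between 10% and 50%.

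**Step 1: information kept by a cut on change.** Relative to the difference in mean change, a cut that a share p exceeds keeps φ(z)² / [p(1 − p)], where z is the normal quantile at 1 − p and φ the normal density.

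| p | z | φ(z) | Kept | Lost | 60 people count as | 40 people count as |
|---|---|---|---|---|---|---|
| 50% | 0 | 0.399 | 0.159/0.25 = 0.637 | 36% | 38 | 25 |
| 30% | 0.524 | 0.348 | 0.121/0.21 = 0.576 | 42% | 35 | 23 |
| 20% | 0.842 | 0.280 | 0.078/0.16 = 0.490 | 51% | 29 | 20 |
| 10% | 1.282 | 0.175 | 0.031/0.09 = 0.342 | 66% | 21 | 14 |

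Under normality 36% is the smallest loss for any cut. A stricter cut loses more (78% at p = 5%).

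**Step 2: cross-check at a finite effect.** For an assumed difference of 0.5 SD, at two-sided 5% and 80% power, the mean comparison needs 63 per arm. The rate comparison needs 102 per arm if 50% of KN-only respond and 152 if 10% do. The saving is 1 − 63/102 = 38% to 1 − 63/152 = 59%, in line with Step 1.

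**Step 3: illustration at this trial's size.** Simulation with 20,000 replicates, Time 1 to Time 2 correlation 0.7 (assumed), and 20-30% of KN-only responding (assumed). Power at two-sided 5% serves only as a measure of information, since no test is planned.

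| Per arm | Difference (SD of change) | Mean change | Baseline-adjusted score | Responder rate |
|---|---|---|---|---|
| 30 | 0.50 | 48% | 53% | 30-32% |
| 30 | 0.65 | 70% | 76% | 47-51% |
| 20 | 0.65 | 52% | 57% | 34-35% |

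**Step 4: transfer into a range.** The second and third statements are not cuts on change. Only someone who starts outside the range can move into it, so those already inside add nothing. With everyone counted, 30 per arm and 0.5 SD, simulated power was only about 14-19%. This depends on where the boundary lies relative to baseline scores, which the protocol does not give, so it indicates direction rather than size.

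**Step 5: what a visual reading would show.** With a true benefit of 0.5 SD of change and 30 per arm, the responder-rate difference is zero or in the wrong direction in about 8-9% of trials, against about 2% for the baseline-adjusted score and 3% for mean change. At 20 per arm, with 20% of KN-only responding, it is about 15-16% against 6% for mean change.

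**The case against.** The strongest reply is that these are hypotheses and expectations, not an analysis plan. Nothing says the RBANS will be analysed only as yes/no. The general method text speaks of comparing groups before and after, the full battery is given, and an SAP that is not shown may well analyse the score. Much of this stands: the loss is not built into the data and can be recovered. But one of the three statements sits under Study Endpoints, and all three choose the same kind of measure. That is a choice the protocol states, not a detail it leaves open, and an SAP that led with the score would depart from it.

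Second, no test is planned, the primary objective is feasibility and acceptability, and no go/no-go decision hangs on the RBANS. This also stands. A reader might infer from the power figures that a planned comparison is underpowered; the protocol plans none. What remains is imprecision, and Step 5 shows that it affects a visual reading too.

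Third, a rate of meaningful improvement is relevant to patients in a population chosen for its risk of decline. That is a good reason to report the rate, but it does not require the rate to lead.

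Finally, a reader might infer that the RBANS is the only outcome cut this way. The documents do not support that. Both the Objective 2 expectations and Study Endpoints also state ketones as a rate at a threshold, and the opening phrase of the Objective 2 hypothesis could be read as governing its whole list of outcomes. The point does not need that contrast.

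**Conclusion.** The point holds as one about the precision of a secondary signal. Every statement of the expected RBANS effect is a rate, although the total score is collected. With roughly normal scores and 10-50% of participants responding, a cut on change loses about 36-66% of the information, and transfer into a range probably loses more. That range is conditional: it should not be read as a property of this trial, because the protocol gives no cut, SD or responder rate. The power and wrong-direction figures further assume a correlation of 0.7 and effects of 0.5-0.65 SD of change, and are illustrations only. The change is worth making because it is nearly free, but the feasibility aims do not depend on it.

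**What to change.** In the Objective 2 hypothesis, the expectations paragraph that follows it and section 4.0, state the lead RBANS signal as the between-arm difference in total scale score at Time 2, adjusted for the Time 1 score and shown with a confidence interval. An interval fits the decision not to test. Give the same comparison at Time 3 for those tested in person, and say that remote completers have no RBANS then. Keep the rates of improvement or transfer beside it as supporting description.

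The cost is wording in three places. No new data, visits or participants are needed, and nothing now reported is lost.

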### **3.0 Background\***

Alzheimer's disease (AD) is the fifth leading cause of death in the United States, and despite decades of research, there are still no effective treatments or preventive interventions. One promising intervention has been nutrition that mimics calorie restriction, such as ketogenic nutrition (KN). Ketogenesis appears to be one of the primary pathways through which calorie restriction provides benefit. Thus, nutritionally dense KN provides many of the physiological benefits of calorie restriction while providing sufficient satiation and nutrition. Specifically, KN may directly target neurobiological mechanisms associated with the development of AD, such as defects in mitochondrial function, cerebrospinal fluid biomarkers, and dysfunctional glucose and lipid metabolism.

Recent feasibility trials of KN in older adults demonstrate substantial improvements in cognitive scores and mood, suggesting that KN is a promising therapeutic for targeting multiple disease markers associated with AD. Ketogenic nutrition (KN) is also a promising intervention that may directly target mechanisms associated with pain in older adults. In fact, in addition to targeting mechanisms associated with chronic pain, KN is associated with a range of benefits across multiple chronic conditions often associated with pain. Despite being a promising intervention, there are significant barriers to testing and implementing nutritional interventions to prevent AD in real-world settings. One of the most challenging barriers is the difficulty of adhering to long-term diet modification, which may be especially challenging to implement in older adults with mild cognitive impairment (MCI).

Clinical psychology offers multiple empirically supported techniques for changing behavior and thinking and maintaining change. Cognitive behavior therapy (CBT), specifically, has documented success in application to adherence to weight loss and diabetes prevention and treatment programs and can be combined with motivational interviewing (MI) strategies to enhance motivation and adherence to lifestyle change programs. MI-CBT skills can be used in a group setting to improve the scale-up of interventions while providing social support and accountability.

Thus, group-based MI-CBT may be key to pragmatically increasing patient adherence to ketogenic nutrition long-term. In sum, the scientific premise is that adherence to nutritionally dense KN may be a powerful therapeutic for older adults with cognitive impairment; however, there remain significant challenges to testing and disseminating a KN intervention on a larger scale. The proposed project will address these challenges by pragmatically assessing the effectiveness of a telehealth KN adherence (KNA) program embedded in a community clinic, FSU SeniorHealth™, on cognitive and health outcomes.

My project will build on basic science and existing feasibility trials to assess whether a KNA program increases adherence and retention in KN intervention studies, while influencing important clinical and patient-oriented outcomes. Further, we will pilot an embedded pragmatic clinical trial (PCT) approach in order to prepare for a full-scale PCT.

Key innovations include:

- Testing the application of MI-CBT behavioral techniques to address major challenges of promising nutrition interventions in older adults with MCI. The MI-CBT skills portion is designed to enhance motivation and remove personal barriers to eating healthy, while reducing conflicts at home and providing a supportive environment.
- Applying a centralized telehealth delivery model in the context of the community and a senior health clinic to assess the feasibility of delivering this type of health-behavior intervention. We will use a centralized delivery model to increase the scalability and fidelity of the intervention and to reduce clinician burden. This pilot will provide data on the feasibility of using an embedded PCT approach to translate our KNA program directly to the community.
- Utilizing existing, embedded clinic data from EHRs to improve the scalability, reduce costs, and reduce the burden on clinicians and patients for completing clinical research. Through the examination of existing data in EHRs, we will be able to reduce study costs for assessment appointments, measures, and researcher and clinician time.

